- Self-Reported Use of Pain Treatment Services(129): The PMC3’s phenotype and outcomes workgroup developed the “Use of nonpharmacological and self-care approaches” questionnaire to collect information about patients’ use of 13 different pain treatments. The instrument was modified for this study to collect information over the past 3 months (instead of past year), and to include several additional categories. In order to assess costs of services as a result of counseling, we included questions asking, for each treatment received, if it was in an individual or group setting and if the treatment was done at home (self-care). We will also ask if the treatment was received at the VA or an “other” provider and the number of times in the past three months it was received. Categories include evidence-based and complementary and integrative modalities for pain available at VA sites and in the community, and include (1) over-the counter medications (2) opioid medications for pain (3) other prescribed medications for pain (4) ER/urgent care visits for pain (5) primary care doctor visit for pain (6) surgery for pain (7) spinal cord stimulator (8) injection for pain (9) TENS (10) Acupuncture (11) dry needling (12) Acupressure (13) manipulation of spine or joints (14) massage therapy (15) yoga (16) tai chi or Qigong (17) Reiki (18) Biofeedback (19) education about how to cope with pain (20) counseling for pain (21) relaxation techniques for pain (progressive relaxation, guided imagery, visualization, deep breathing) (22) mindfulness or meditation (23) hypnosis or hypnotherapy (24) walking to help with pain (25) exercises like aerobics, strength training or stretches to help with pain, (26) other treatments for pain

Substance Use Measures:

- ASSIST. Substance use will be measured over the last 3 months using Version 3.1 of the Alcohol, Smoking and Substance Involvement Screening Test (ASSIST). After a screening question focusing on substances ever used, the ASSIST consists of seven questions about use of and consequences of use of each of ten classes of substances over the preceding three months (including nicotine). Scores are generated for each substance that are mapped to a three-point ordinal scale of severity.(131) As outlined in the World Health Organization’s Manual describing the use of the ASSIST to guide treatment recommendations, the ASSIST ratings are scaled to represent no need for treatment, need for a brief intervention, and need for an intensive intervention. An advantage of the ASSIST is that these categories represent what clinicians consider a clinically important difference, in that they guide treatment recommendations. The items in the ASSIST have been shown to have good to excellent reliability for the substances assayed. The reliability of the individual ASSIST items,(132) and the ASSIST’s concurrent validity compared to other more detailed assessments of substance use severity(133) have justified its adoption by the World Health Organization.(134) We will obtain additional specifiers for substances requiring further characterization: a specifier about use of vaping for tobacco products, a specification as to whether the Veteran is using legal or prescribed cannabis and specification about use of prescribed amphetamine.
- Prescription Opioid Misuse Two questions,(135) adapted from the CIDI(136) for use in a NIDA Clinical Trials Network study,(137) will be used to describe misuse of prescribed opioid medications: “How often have you taken your pain medications in larger

amounts than prescribed or for a longer period than prescribed?" and "How often have you used your pain medicines to get high, to relax, or to make you feel more alert?" The questions are asked about the preceding 4 weeks, with follow-up questions to clarify that the question refers to opioids only.

- Nail Collection and Measurement: Nail clippings will be assayed for metabolites of alcohol (ethyl glucuronide i.e. ETG), cannabinoids (carboxy-THC, native-THC), opioids (6-MAM, codeine, hydrocodone, hydromorphone, morphine, oxymorphone, oxycodone), Amphetamines (amphetamine, MDA, MDEA, MDMA, methamphetamine), Cocaine (benzoylecgonine, cocaethylene, cocaine, norcocaine) and Phencyclidine (PCP). The tests are highly specific. Samples are analyzed using an immunoassay technique (ELISA) and non-negative specimens are subjected to a gold standard confirmation technique (GCMS or other method, depending on drug class). Nail, like hair, traps biomarkers in keratin but has higher concentrations of neutral and acidic biomarkers because it has thicker keratin. In a study of hair and nails collected from the same people, the rate of Carboxy-THC (an acidic biomarker for cannabis) positives for cannabinoid at the SAMHSA-recommended cutoff was 46.7% for hair and 53.3% for fingernails and mean concentrations of the metabolite were five-fold higher in nails than in hair.(138) In a study in the journal *Addiction* of 606 college students,(139) nail ETG at the 8 pg/mg threshold proposed for this study detected high-risk drinking with a sensitivity of 1.0 and a specificity of .63. Receiver operating characteristic curves were significantly higher for ETG concentration in fingernails than in hair for detecting risky drinking. The biomarkers are incorporated throughout the nail plate from base to tip, by deposition of biomarkers from the capillary rich nail bed, thus allowing measurement by any nail clipping of sufficient weight. Biomarkers are thought to reflect 3-6 months of substance use history in fingernails, and toenails, which grow more slowly, reflect up to 9 months. The detection window (3-6 months) is close to the timeframe of the ASSIST (90 days), making cross-validation by the two measures reasonable.

Approximately 100 mg of nail is required for analysis, which can be obtained from 2mm (a quarter's width) of nail from each of ten digits. Samples will be mailed from home and thus un-observed, and participants will be provided with kits for the nail clipping, and a financial incentive of \$30 for providing each of the samples. We will also suggest Veterans set reminders to allow for growth before clippings are needed.

To reduce the risk that Veterans pass off someone else's fingernails as their own, they will be asked if the nails are theirs, and paid regardless of whether they are. Specimen substitution when there are contingencies for positive urines occurs, but there is no incentive for such false reporting when payment is provided regardless of the sample results. The samples will be mailed in coded envelopes addressed to our group, further reducing the likelihood of submitting someone else's fingernails.

Samples will be processed at the United States Drug Testing Laboratories (Illinois). After processing, samples will be destroyed following a standard storage period. Sample analysis uses fully validated methods that have been inspected and approved by the College of American Pathologists Forensic Drug Testing Program and the New York State Department of Health.

- Substance Use/Mental Health Treatment Service Utilization-VA Records: Visits from the EHR involving substance use and mental health treatment will be identified conservatively, using an algorithm involving workload information entered at clinic visits (e.g. diagnosis treated, procedure performed) and the type of clinic providing the treatment. The measure does not capture much substance abuse counseling in primary care settings, and in conjunction with other mental health treatment (i.e. PTSD treatment). For this reason, self-reported substance use service utilization will be collected (see below).
- Self-Reported Use of Substance Use Treatment Services: Using the same format as the pain treatment service use questions described above, we will inquire about whether each of a number of classes of treatments was received in the preceding 12 weeks (substance use counseling, day program, residential, ER/hospital, self-help, counseling at a medical visit, counseling at a visit for a psychiatric condition, opioid substitution, smoking cessation counseling, nicotine replacement therapy prescribed), how many times each treatment was received in a group/individual setting, and if the service was provided by the VA or other.
- Alcohol Use Disorders Identification Test (AUDIT-C)(140). This is an alcohol screen used to identify patients who are hazardous drinkers or have active alcohol use disorders (including alcohol abuse or dependence). It consists of three questions: "how often did you have a drink containing alcohol in the past year?", "how many drinks did you have on a typical day when you were drinking in the past year", and "how often did you have six or more drinks on one occasion in the past year". It is scored on a scale of 0 (no use) through 12. In men, a score of 4 or more is considered positive and in women, a score of 3 or more is considered positive.
- Prescribed Opioids or Stimulants: Certain prescribed medications will make fingernail testing results come up positive. To determine whether a positive nail toxicology result is due to illicit use or due to a prescribed medication, we will ask two questions: In the past 12 weeks have you been prescribed (1) opioid medications such as codeine, Vicodin, oxycodone, fentanyl, morphine, methadone, or suboxone? (2) Amphetamine-type stimulants such as Ritalin, Dexedrine, Adderall, Vyvanse, Concerta, or methylphenidate?"

Other Measures:

- Patient Health Questionnaire (PHQ-9): The PHQ-9 is a well validated screening measure for depression(141) and will be used to identify probable depression as a covariate in analyses. It will also identify suicidal ideation, which if severe, will trigger the need for further assessment (detailed in Human Subjects).

- EQ-5D-5L(142). The EQ-5D-5L is a standardized measure of health status designed to provide a single index value of health for clinical and economic appraisals. It consists of five questions in the domains of mobility, self-care, usual activities, pain/discomfort, and anxiety/depression
- Work Productivity and Activity Impairment Questionnaire-General Health (WPAI-GH Interviewer Versions)(143). This assessment measures the effect of general health and symptom severity on work productivity and regular activities during the past seven days. It consists of six questions. Q1 asks if currently employed. Q2 asked hours missed due to health problems, Q3 asks about hours missed for other reasons, Q4 asks about hours actually worked. Q5 asks the degree health affected productivity while working. Q6 asks the degree health affected productivity in regular unpaid activities.
- Motivation for engaging in pain treatment(144, 145). Motivation for change scale to include 3 items (analogue scale coded from 1 to 100) tapping patient likelihood to engage in pain services, recognition of pain treatments as important, and pain treatment motivation.
- COVID-19 questionnaire. These questions will assess participant infection status, and the effect that COVID-19 regulations have had on Veterans' access to pain treatment and substance use treatment.

Other Measures Collected in UG3 Phase and then again at the end of the UH3 Phase:

- Relational Coordination Survey. This survey, as previously described in the UG3 phase, will be administered post-trial to "hub" SBIRT-PM counselors and "spoke" clinical and administrative staff in Compensation and Pension and Primary Care to examine how pain care was coordinated to meet the treatment needs of compensation-seeking Veterans. The survey will again be administered online through VA REDCap. Attempt will be made to have the same staff members who completed the survey in the UG3 phase completed the survey again at the end of study. If VA staff are not available or interested in completing the survey again, site PIs will identify additional VA staff providers.
- Post-Trial Semi-Structured Qualitative Interview. At the end of the trial, using the same interviewing procedures noted in the UG3 phase, we will conduct in-depth interviews with "hub" SBIRT counselors and "spoke" clinical and administrative staff in Compensation and Pension and Primary Care to assess the organization and coordination of pain management services, given their experiences with SBIRT-PM implementation.

Data Analysis

To examine feasibility of enrollment, counseling participation, and pilot study retention, descriptive data (frequency counts, percentages, means, and standard deviations) were calculated. Descriptive data were also provided for study outcomes. Changes in BPI scores and the number of nonpharmacological pain treatments utilized from baseline to week 12 were calculated and examined using the Wilcoxon signed rank sum test, the nonparametric equivalent of the paired *t*-test. The percentages of participants with problematic substance use were compared between baseline and week 12 using χ^2 tests. The *p* values should be interpreted with caution given lack of a control group and limited statistical power. For qualitative analysis, transcribed interviews were analyzed using standard qualitative analysis methods by which 2 coders independently reviewed the transcripts, creating code definitions as concepts emerged inductively from the data. Codes were refined until a final coding structure was reached, capturing the major concepts in the data, which was then applied to all transcripts.

Analysis of Qualitative Data.

We hypothesize that implementation of SBIRT-PM will be associated with changes in the way staff interact with each other, how they think about pain treatment, and how they connect service-connection claimants to treatment. To test these hypotheses, we will compare results from the Relational Coordination Survey administered before the RCT with survey results from the same participants afterwards using paired-samples *t*-tests. The comparison of semi-structured interviews with stakeholders and staff before and after the RCT will involve describing differences in themes identified at the two timepoints.

Analyses of NLP Algorithms

We will identify the use of non-pharmacological pain modalities through self-report from the participants as well as two different approaches to the extraction of healthcare utilization data from electronic medical records. Medical record extraction of 1) Structured data - stop codes indicating use of these modalities, and 2) Unstructured data - domains identified in the application of the NLP method to the medical record data of study participants. Two independent researchers will identify words/snippets that suggest use of specific non-pharma modalities and rate enough snippets to have software reliably generate an algorithm to rate all patients included in the study on each modality (machine learning). As we expect false positive reports of use of a modality to be unlikely, identification of use during an assessment period by any of the three methods (self-report, medical record stop codes and NLP) will be considered use. The agreement between these different measures will be described by crosstabs.

References

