Working with the VA PACT structure, the SBIRT-PM counselors will facilitate Veterans connection with their teams, or initiate the process of getting Veterans not currently receiving VA-based primary care registered, so that consults for multi-modal care can be placed. The SBIRT-PM counselors and the nurse case managers will need to collaborate to engage Veterans in non-pharmacological pain management care over time. The coordination between the SBIRT-PM counselor and the people making pain management referrals may vary within and across the eight spoke sites. We have detailed six milestones below reflecting the establishment of hub and spoke relationships needed for SBIRT-PM. The relationships are among SBIRT-PM trial investigators, SBIRT-PM counselors, nurse case managers and other people who arrange pain treatment, and Compensation and Pension Clinic stakeholders. We will conduct a mixed methods formative evaluation to inform how we coordinate relationships between the hub and spoke sites and make site-specific adaptions to SBIRT-PM.

3. Establish SBIRT-PM investigative team meeting structure

Within the first two months of this project, Drs. [name] and [name] will establish weekly investigative team meetings involving the core hub-based investigators ([name], [name], [name], [name], [name]) and Site-PIs. These meetings will focus on initiating the planning phase of the study and achieving the major UG3 milestones. To avoid the tedium of too-large conference calls, we will use suggested procedures such as familiarizing participants with each other, a written agenda, and respecting participants' time by only requesting their attendance when it is needed. In addition, we will establish separate cores to address specific areas requiring focused planning, with membership dictated by expertise and designated duties: 1) cost estimation methods ([name], [name]); 2) mixed methods formative evaluation ([name], [name], [name]); 3) natural language processing algorithms ([name], [name], [name]); and 4) SBIRT-PM adaption ([name], [name]). Core meetings will occur on a biweekly basis, and Drs. [name] and [name] will participate in each core.

4. Establish procedures to communicate contact information of Veterans applying for compensation from spokes to the hub

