The counselor's explanation of the role of opioid medications paraphrases messages that primary care providers deliver to Veterans as part of [name] safe prescribing approach.(113) The counselor explains that medications, including both opioid and non-opioid medicines, have an important place in some Veterans' pain treatment, and that Veterans benefit when pain medicines are prescribed and taken safely. The counselor reinforces the importance of taking opioid medicines as prescribed because there are risks of addiction and interactions with other substances (like alcohol). The counselor explains that judicious use of non-opioid medications improves pain treatment outcomes without these risks.

The counselor introduces the idea that non-pharmacological treatments can help manage pain, and explains what they are and how they work. These services may include: (1) treatment for the underlying ailment, (2) physical therapy (both at VA and as home exercise and stretching programs), (3) behavioral treatments like Cognitive Behavioral Therapy for chronic pain, (4) treatments for depression, PTSD, and/or other mental health problems that chronic pain may have aggravated, and (5) complementary and integrative health interventions available including chiropractor services, acupuncture, and yoga.

Throughout these discussions, the counselor seeks opportunities to motivate the Veteran to engage in multi-modal pain care using a variety of MI consistent approaches. If the Veteran commits to engaging in pain management services, the counselor develops a plan with the Veteran to initiate this process. For Veterans not enrolled in VA services, the counselor explains the procedures to obtain eligibility for VA care.

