We also will collect other data about SBIRT-PM implementation. Specifically, we will report the percentage of participants who received different "doses" of the intervention (i.,e., 0, 1, 2, 3, or 4 sessions). We also will track the percentage of each counselor's assigned Veterans who receive counseling and the percentage whose first counseling session is followed by a second. In our pilot, 80% of participants received the assigned counseling, and 55% of those who received any counseling had at least two sessions. If a counselor falls below 70% of participants receiving any counseling within 12 weeks or below 50% of a second session among those with a first, we will take the following steps: 1) compare that counselor's procedures to "best practices" by other counselors. Such best practices might include time of day Veterans are called, and the negotiation around scheduling the calls; and 2) contact the site PI to determine if sub-optimal engagement is a site-specific issue. Two examples of site-specific issues are cell phone reception and local VA hospital reputations. In very rural areas, poor cell phone coverage makes participation more difficult, and it may be more difficult to engage Veterans when the VA facilities in their local communities have a damaged reputation.

Finally, using the ITRS, we will independently rate a random sample of about 10% of the SBIRT-PM sessions (n = 220) for the counselors' adherence and competence in delivering the intervention to demonstrate the sessions were delivered as intended.

Study Evaluations

Assessments

Assessment Name/Domain	Data Source	Baseline	12-wk	Time to complete (mins)
Socio-demographic Characteristics	Self-Report	x		2
Psychiatric and Substance Use Diagnoses	VA EHR -structured data (e.g. clinic codes)	x		
Characteristics of Musculoskeletal Disorders	VA EHR, Service-connection exam	x		
Distance to nearest VA Facility	VA EHR		x	
Brief Pain Inventory	Self-report	x	x	5
PEG	Self-report	X	X	1
High Impact Pain questionnaire	Self-report	X	X	1
Opioid Medications Dispensed in Morphine Equivalent Daily Dose	VA EHR	x	x	
Non-opioid Medications Dispensed	VA EHR	x	x	
Pain Management Service Use—VA services	VA EHR -structured data (e.g. clinic codes)	x	x	
Pain Management Service Use---VA and non-VA services	VA EHR with Natural Language Processing	x	x	
Self-reported VA and non-VA service use	Self-report	x	x	3
ASSIST	Self-report	x	x	10
Prescribed Opioids or Stimulants	Self-report	x	x	2

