- PEG(128). The PEG is a 3-item scale assessing pain intensity (P), interference with enjoyment of life (E), and interference with general activity (G) during the past week. It has good reliability, constructive validity, and sensitivity to change and has been required by the NIH-DoD-VA Pain Management Collaboratory Coordinating Center as a common measure across funded protocols.
- High Impact Pain Questions(129): Three questions to determine the long-term impact of pain are being asked. "In the past 3 months, how often did you have pain?"; "Over the past 3 months, how often did pain limit your life or work activities"; "Are you not working or unable to work due to pain or a pain condition?". Answer choices consist of "never", "some days", "most days" or "every day" for the first two questions and yes/no for the third question.

Pain Treatment Services Received:

- Opioid Medications Dispensed. We will extract dispensed opioid medications and dosages from the patient's electronic medical record and convert them to morphine equivalent daily dose using the procedures from a published algorithm.(130) as adopted and operationalized by the PMC3 Phenotypes and Outcomes workgroup. Medications will be classified as opioids used to pain as follows:
 - (1) All non-IV fills of:
 - a) Codeine
 - b) Fentanyl
 - c) Hydrocodone
 - d) Hydromorphone
 - e) Morphine
 - f) Oxycodone
 - g) Oxymorphone
 - h) Tramadol
 - (2) All non-IV, pill/tablet pills of

- a) Methadone
- (3) All transdermal or buccal fills of
 - a) Buprenorphine

MEDD is calculated by assuming prescriptions were taken as directed. Total morphine equivalents are calculated by multiplying the quantity of each prescription by the strength of the prescription (milligram of opioid per unit dispensed). Standard conversion factors on the CDC website will be used to estimate the number of milligrams of morphine equivalents dispensed. Average daily morphine equivalent dose will be calculated by dividing total milligrams of morphine equivalents by days supplied. For prescriptions that span a particular month, only dates during that month will be included.

The PMC3 Collaboratory recommends the following be collected, and we will collect and analyze them per their recommendations:

- a. Number of opioids supplied
- b. Days supplied
- c. a/b x conversion factor = milligrams morphine equivalent daily dose (MEDD)
- d. Mg MEDD at enrollment
- e. Mg MEDD monthly during enrollment and at study completion.

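### Opioid dose and non-opioid drug classes are read only from VA dispensing while SBIRT-PM helps Veterans into VA care, so unchanged outside use can later appear as new use

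*Combined protocol and SAP*

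**What the plan says.** **Source of the medication measures.** Under Pain Treatment Services Received, the opioid entry reads: "We will extract dispensed opioid medications and dosages from the patient's electronic medical record". The Assessments table lists "Opioid Medications Dispensed in Morphine Equivalent Daily Dose" with the VA electronic record as its only source, at baseline and at 12 weeks. The row for non-opioid medications is sourced in the same way, and each of those classes is scored as present or absent.

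**Dose rule and time points.** "Average daily morphine equivalent dose will be calculated by dividing total milligrams of morphine equivalents by days supplied". The values to be collected are "Mg MEDD at enrollment" and "Mg MEDD monthly during enrollment and at study completion".

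**Who can take part and what the counselor does.** The UG3 inclusion criteria ask for a filed claim, a pain score and a telephone; VA enrollment is not among them. Section 2 (hub-and-spoke coordinated relationships) says counselors will connect Veterans with their teams or "initiate the process of getting Veterans not currently receiving VA-based primary care registered". The Initial Session text adds: "For Veterans not enrolled in VA services, the counselor explains the procedures to obtain eligibility for VA care". The Background section on the hub-and-spoke model treats new VA enrollment as a possible result of SBIRT-PM.

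**Other opioid data.** The self-reported pain treatment questionnaire includes "2) opioid medications for pain (3) other prescribed medications for pain", asked at both visits, with VA or other provider and number of times over three months. A separate item asks whether opioids were prescribed in the past 12 weeks; its stated purpose is to interpret nail toxicology. Nail clippings are also assayed for opioids.

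**The concern.** Change from baseline in a dispensing measure is meaningful only if dispensing is seen equally well at both times. Here the record is the VA's own, and one aim of the counseling is to bring Veterans into the VA. A Veteran on an outside opioid who transfers to a VA prescriber at the same dose goes from unseen to seen. A Veteran who stops an outside opioid shows no reduction. Both errors work against SBIRT-PM. A mistaken report that a non-pharmacological pain program was followed by more opioid prescribing would be awkward for the trial that the pilot is meant to prepare.

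The plan deals with this kind of gap elsewhere. Claims data supplement VA diagnoses, self-report supplements VA records of substance use treatment, and Analyses of NLP Algorithms counts a non-pharmacological modality as used if any of three sources shows it. No such rule covers medications.

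**Working it through.** The plan states no figure for this point, so there is nothing to reproduce. The check sets the rules side by side and then gives an illustration.

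1. **Baseline, opioid taken only from outside VA.** The dose rule is total mg of morphine equivalents divided by days supplied. With no VA fill this is 0 mg / 0 days, which is undefined. The text does not say whether it becomes zero or missing. Coded zero, the outside dose is recorded as none. Coded missing, the Veteran drops out of the change, and so does every true non-user without a VA fill. Either way the outside dose is not counted.

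2. **Baseline, non-opioid class taken only from outside VA.** The measure is binary and comes from the VA record, so the class is recorded as absent.

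3. **Follow-up.** If prescribing has moved to VA by week 12, the fill is visible. True change is zero. Recorded change is a new drug class or, with zero coding, a rise in MEDD.

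4. **Can the other data correct this?** In part. The self-reported items show opioid use at both visits, and the pain questionnaire also asks whether the source is VA or other. They give no drug, strength or dose and are not monthly. The item on other prescribed pain medication does not identify a drug class. No rule links any of them to MEDD.

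5. **Illustration; every input except N is assumed.** Let q be the share with opioids only from outside VA at baseline, t the fraction of these whose fills move to VA by week 12, and D their unchanged dose, with no VA fill coded as zero. Apparent new users = N × q × t. Spurious mean MEDD rise = q × t × D. N is 5 × 8 = 40 (Specific Aims) or up to 10 × 8 = 80 (section 11).

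| Assumed q, t | New users, N = 40 | New users, N = 80 | MEDD rise, D = 20 mg/day | MEDD rise, D = 50 mg/day |
|---|---|---|---|---|
| 5%, 25% | 0.5 | 1 | 0.25 | 0.62 |
| 10%, 50% | 2 | 4 | 1.0 | 2.5 |
| 20%, 100% | 8 | 16 | 4.0 | 10 |

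The range of 0.25 to 10 mg/day, against a true change of zero, reflects the assumptions and nothing measured.

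**The case against.** The strongest reply is that the measure is named for what it is: medications dispensed, from the VA record. The plan does not present it as total exposure. It also defers to a published algorithm and to a collaboratory workgroup's recommendations, which may contain a rule for no fills and cannot be checked here. Data Analysis tests only BPI scores, the number of non-pharmacological treatments and problematic substance use. MEDD is not named there, so at most it would be described, and the section already urges caution because there is no control group. Self-report and nail assays could expose a false new user. Transfer within 12 weeks may also be uncommon: the first session follows the compensation examination, and counselors cannot place even consults.

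Most of this stands, and it limits the consequence. It does not remove the gap, because a baseline-to-week-12 change in VA dispensing will be read as a change in prescribing unless the report says otherwise.

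Three stronger readings are tempting, and the documents support none of them.

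- A reader might infer that outside opioids are recorded as a zero dose. For MEDD that is only one of two possible codings.
- A reader might infer that in the later comparison with usual care only the SBIRT-PM arm would move into VA care. The Background says that Veterans judged service-connected receive priority VA care, and all participants are claimants, so usual-care Veterans may enter too.
- A reader might take a particular spurious rise as an estimate. The share of outside users, their dose and the rate of transfer are all absent from the documents.

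**Conclusion.** The concern holds in a limited form. Both medication measures come only from the VA record, the pilot can include Veterans outside that record, and the intervention helps them into it. Baseline-to-week-12 change therefore mixes change in use with change in visibility, and no rule separates the two. For non-opioid classes this follows directly from the binary measure. For MEDD it depends on a no-fill coding that is not stated.

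The size cannot be derived from the documents. With no control group, the artefact could not be told apart from real change within the pilot. It bears on a secondary, descriptive measure and not on the BPI or the tested outcomes. A between-arm difference in the later trial is possible, but its size is unknown. This is a cheap improvement to make and does not undermine the pilot.

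**What to change.** 1. Label MEDD and the drug-class measures as VA-dispensed only, and state how a Veteran with no VA fill is coded.
2. Report baseline-to-week-12 change separately for Veterans who were and were not receiving VA care at baseline, with that status defined in advance. Do not read a rise in the second group as new use.
3. Use self-reported opioid use, VA or other, from the pain treatment questionnaire, together with the 12-week prescribed-opioid question, as the all-source measure of change in opioid use. Cross-tabulate it against VA dispensing over the same look-back at baseline and week 12. This follows the any-source rule that the plan already applies to non-pharmacological modalities.

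Setting VA MEDD to missing when self-report shows an outside opioid without a matching VA fill is not recommended. Self-report gives no drug or dose, so a match cannot be established.

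The cost is analysis and reporting text, with no new participant questionnaires. The drawbacks are small subgroups in a pilot of 40 to 80, and an all-source measure that shows use but not dose. It cannot correct monthly MEDD or identify a non-opioid drug class.

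### The listed MEDD formula omits unit strength, so it differs from the plan's own narrative definition by a factor equal to the milligrams per unit

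*Combined protocol and SAP*

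**What the plan says.** The derivation is in the combined protocol and SAP, under Pain Treatment Services Received, in the entry Opioid Medications Dispensed. That entry contains two rules.

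- **Narrative paragraph.** Total morphine equivalents come from "multiplying the quantity of each prescription by the strength of the prescription (milligram of opioid per unit dispensed"). CDC conversion factors are then applied, and the daily average is obtained by "dividing total milligrams of morphine equivalents by days supplied".
- **Itemised list, directly below.** It is introduced by "The PMC3 Collaboratory recommends the following be collected, and we will collect and analyze them per their recommendations". Its first two items are "a. Number of opioids supplied" and "b. Days supplied", and the third is "c. a/b x conversion factor = milligrams morphine equivalent daily dose (MEDD"). Items (d) and (e) then call for MEDD in milligrams at entry, monthly, and at the end of the study.

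No sentence says which rule governs if they differ. The assessment table schedules MEDD from the VA record at baseline and week 12.

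**The concern.** The two rules are presented as the same quantity but do not have the same units. The narrative yields morphine milligrams per day. Item (c) divides a count by days and applies a factor, yet its result is labelled milligrams.

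A programmer who codes the list literally would produce a variable with the wrong level. The error would differ by product, because unit strength differs, so no single rescaling would repair it afterwards. The variable would also fail to register a dose change made by switching to a stronger or weaker unit. It could show a change where the daily dose had stayed the same and only the tablet count had altered. What is at stake is the description of dispensed opioid dose at entry, by month and at completion.

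**Working it through.** The documents state no numerical MEDD, so there is no figure to reproduce. The check is a comparison of units and a direct calculation of both rules.

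**Inputs.** From the plan: the two formulas above. Assumed for illustration, because the documents give no fill data and no factor values: a 30-day supply; Q = 60 units unless stated; strength S of 5, 10 or 20 mg per unit; conversion factor F of 0.5, 1, 1.5 or 4.

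**Formulas**, with Q = units supplied and D = days supplied:

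- Narrative: N = Q × S × F / D. Units: (units × mg/unit × morphine mg per mg) / days = morphine mg per day.
- List item (c): L = (Q / D) × F. Units: factor-weighted units per day.
- Ratio: N / L = S. Q, D and F all cancel.

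**Numbers, Q = 60 and D = 30:**

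| F | List item (c), any strength | Narrative, 5 mg | Narrative, 10 mg | Narrative, 20 mg |
|---|---|---|---|---|
| 0.5 | 1 | 5 | 10 | 20 |
| 1 | 2 | 10 | 20 | 40 |
| 1.5 | 3 | 15 | 30 | 60 |
| 4 | 8 | 40 | 80 | 160 |

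In every row the ratio of narrative to list is 5, 10 or 20, which is the unit strength.

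**Change over time, F = 1 and D = 30:**

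- Strength doubled, count fixed (60 × 5 mg to 60 × 10 mg): the narrative goes from 60 × 5 / 30 = 10 to 60 × 10 / 30 = 20 mg/day. Item (c) stays at 60 / 30 = 2. A real doubling is not seen.
- Same daily dose, different units (60 × 5 mg to 30 × 10 mg): the narrative is 10 mg/day both times (60 × 5 / 30 and 30 × 10 / 30). Item (c) goes from 60 / 30 = 2 to 30 / 30 = 1. A halving appears that did not occur.

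**When item (c) would be right.** Inserting S gives (Q × S / D) × F, which is the narrative rule. As written, the line is correct only if item (a) means milligrams supplied, or if the factor already contains unit strength. The text says neither, and the narrative treats quantity, strength and factor as three separate terms.

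**The case against.** The strongest reply is that a workable definition stands immediately above the list. It includes strength and is dimensionally sound, and the milligram labels in items (c) to (e) point the same way. The list also refers to the collaboratory's recommendations, and the entry cites a published algorithm as operationalised by a workgroup. Neither source is reproduced, and item (a) might there mean milligrams.

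Much of this stands. A reader might infer that the plan leaves strength out of MEDD altogether, or that the reported MEDD values are wrong. The documents support neither: strength is in the narrative, and nothing shows which rule was coded.

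What the reply does not do is remove the conflict. The plan never says that the narrative takes precedence. The list carries the commitment ("we will collect and analyze them per their recommendations") and names the quantities to be analysed. A possible meaning in an unseen source does not define a term in this plan.

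A reader might also infer that the narrative would pool overlapping fills and so average their doses instead of adding them. The text does not direct this. Its first step is worded prescription by prescription, and it limits fills that cross a month to the days within that month. Silence on overlap is not an arithmetic error.

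**Conclusion.** The point holds as an internal contradiction. Item (c), followed literally, gives factor-weighted units per day and differs from the narrative MEDD by a multiple equal to the unit strength. That ratio follows from the formulas alone. The 5-, 10- and 20-fold figures rest on assumed strengths, and the absolute values also on assumed quantities, days and factors.

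The reach is limited. A reader might infer that the trial's main results are at risk, but BPI Pain Severity is the primary pain outcome and does not use MEDD. The tests named under Data Analysis concern BPI scores, the number of nonpharmacological treatments and problematic substance use. At most, MEDD falls under the descriptive summaries of this uncontrolled pilot. Nor is it the only opioid information: self-reported use, misuse questions and nail assays are also planned. It is, however, the measure of dispensed dose, so the contradiction is worth removing.

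**What to change.** Rewrite item (c) as: (number of units supplied × strength in mg per unit × conversion factor) / days supplied, for each prescription. Alternatively, add one sentence stating that the narrative definition governs.

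Because the pilot's Data Analysis section is partly written in the past tense, also check which formula was used for any MEDD output already produced, and re-run it if it followed item (c) literally.

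The cost is one line of text and a short programming check. No new data are needed: dosages are already extracted from the record, and the narrative already uses unit strength.
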